1.4 Rationale for the non-significant risk classification of this study

While interfacing with a nerve at a depth of 2 to 3 cm would be a possibility for an early feasibility study, it was determined that a subcutaneous placement of the shortened study device would provide the same biocompatibility data and the same electrical transmission capabilities efficacy data, while subjecting the study participants to a very minimal and controlled amount of Non-Significant Risk (NSR).

Under 21 CFR 812.3(m), an NSR device study is one that does *not* meet the definition for an SR device study. Below we cover all criteria that define an SR device and then detail why the Basmati Injectrode does *not* meet these.

Specifically, as per 21 CFR 812.3(m), an SR device:

- 1. Is intended as an implant and presents a potential serious risk to the health, safety, or welfare of a subject.**

The commercial version of Neurnoff's Injectrode will be an implantable electrode. However, this early feasibility prototype is limited to 28 days of use to avoid risk resulting from long-term implantation duration where regular follow-up is impractical or impossible. Therefore, the Basmati insert does not meet the definition of an implant. In this study, the Basmati will be used to document the clinical biological response after a placement duration of 28 days only. According to FDA guidance, "Use of International Standard ISO 10993, "Biological Evaluation of Medical Devices Part 1: Evaluation and Testing" (2013): a device that makes contact with tissue for a period of time less than 30 days poses considerably lower risk to patients.

- 2. Is purported or represented to be for use supporting or sustaining human life and presents a potential for serious risk to the health, safety, or welfare of a subject.**

The Basmati Injectrode insert is not intended for use supporting or sustaining human life. In the proposed safety study, the device will be temporarily implanted subcutaneously for the purpose of confirming its biocompatibility compared to a previous animal study.

- 3. Is for a use of substantial importance in diagnosing, curing, mitigating, or treating disease, or otherwise preventing impairment of human health and presents a potential for serious risk to the health, safety, or welfare of a subject.**

In the proposed safety study, the Basmati insert will be used as a passive device not intended for diagnosing, curing, mitigating, or treating disease, or otherwise preventing impairment of human health. Prior to removing the device in a minimally invasive procedure, the Injectrode will be briefly interfaced with electrical current using standard electro-acupuncture techniques, following the labeling for these approved devices. The total time of exposure to this limited stimulation period will be approximately 20 minutes right prior to device extraction via Mohs procedure.

- 4. Otherwise presents a potential for serious risk to the health, safety, or welfare of a subject.**

Based on the Neuronoff, Inc. Quality Management System, risks associated with the device will be evaluated and addressed per the Design Control Procedure, SOP-02 and the Risk

Management Procedure, SOP-05 and according with the ISO-14971 Risk Management Standard to assure that the Basmati Injectrode insert is deemed to not represent any potential for serious risk to the health, safety, or welfare of a subject. The minimally invasive placement at a location in the subcutaneous tissue and rigorous follow-up schedule are designed to allow the physician to monitor the response of each study participant very closely and, if necessary, explant the device prior to the 28 day mark without unnecessary risk to the health, safety, or welfare of a subject. The material of the Injectrode is 99.99% gold, a material commonly used in neuromodulation electrodes that is biointert and very well received by humans clinically. The method of removing the Injectrode at the end of the safety study will follow a procedure similar to a Mohs procedure, a standard clinical practice that poses little risk to study subjects. Subjects will be followed for signs of inflammation of the surgical site, granulomas, irritation.

This early feasibility study aims to document the clinical biological response to an Injectrode, roughly the size of a Basmati rice grain, placed temporarily into up to 10 healthy volunteers for a duration of up to 28 days. The efficacy of the device is assessed by measuring electrical and sensory nerve recruitment data immediately prior to explanting the device. These data are intended to provide rationale for a follow-up study testing a therapeutic intervention.

Risk to the study participant is further minimized by placing the study device subcutaneously with the option for a quick minimally invasive explant procedure before the 28 day mark if deemed necessary by the study PI.

This non-significant risk (NSR) study is the first of two early feasibility studies. This first NSR study is designed to subject the study participants to a minimal risk while collecting first human biocompatibility, electrical interface and neurostimulation data.

The expected data set is designed to enable a follow-up study investigating the placement of a longer Basmati-style Injectrode that ranges from the subcutaneous tissue to a nerve located at an approximate depth of 2 to 3 cm deep inside the body. The present BASMATI study mimics the placement into the subcutaneous tissue location and thereby provides the data to enable the follow-up study evaluating a longer Basmati-like electrode to be placed. To minimize risk for participants in the mentioned follow-up study, biocompatibility data and electrical interfacing data are collected in the first NSR study as described in the document in hand.

1.5 Comparison to earlier studies

The Basmati Injectrode will be placed subcutaneously in up to 10 healthy volunteers for a duration of up to 28 days. On the last day of the study, the Basmati Injectrode will be explanted with a margin of approximately 1mm of healthy tissue utilizing a Mohs surgical approach, ensuring maximal study participant safety while enabling the collection of histological samples for chronic human biocompatibility data. Just prior to explanting the device, two very small 30 gauge needles (similar to electro-acupuncture needles) will be placed approximately 5mm into the skin at the location of the subcutaneously placed Basmati, thereby forming an electrical interface with the Basmati. Electrical impedance and stimulation thresholds for subcutaneous afferences (sensory nerves) will be recorded with the two needles and a TENS electrode patch placed extracorporeally at a distance of approximately 10 cm from the Basmati location.

This approach is similar to that utilized with the StimRouter Neuromodulation System, which also consists of an implanted lead with external stimulation equipment to activate the lead transcutaneously^{3 4 5}. Both systems utilize minimally invasive implantation techniques, with the probe injected via hollow stainless steel tubes^{6 7}. However, the Injectrode is different in that it is presented as a gold mesh as opposed to a fixed metal coil, which allows for improved in-body conforming and thus better reach of potentially hard-to-access anatomic targets. Also, in the least invasive use case, the Injectrode can be stimulated via an external TENS unit without requiring an implanted stimulation cable. Thus, the Injectrode offers improved placement potential and functionality with similar or lesser invasiveness than available technologies.

1.6 Study participant safety

Subject safety is our main priority. Accordingly, the devices chosen for this study were selected for their ability to minimize risk. Stimulation will be controlled using an FDA cleared Constant Current Stimulator (DS7A, Digitimer, USA). Impedance will be measured with a handheld, battery-powered oscilloscope (ScopeMeter, Fluke, USA) that is certified and calibrated. Percutaneous interfacing with the Injectrode will be achieved using standard clinical grade sterile 30 gauge needles.

⁷ Bioness® StimRouter™ Neuromodulation System for Chronic Pain Therapy. First Posted May 7, 2012. <https://clinicaltrials.gov/ct2/show/NCT01592344?id=NCT00665132+OR+NCT01592344&draw=2&rank=1&load=cart>

days, n=4). The complete histopathological report is included in the appendix (REC-020). The histopathologist drew the following conclusions:

There was normal fibrous capsule formation, with the most prominent finding being the expected inflammatory response to any implanted material. The fibrotic response was variable – some devices had a higher degree of inflammatory and foreign body giant cells than others. Responses range from +1 to +3 (mild to moderate) responses, the histopathologist stating that this range did not seem concerning and that he assumed it to simply be inter-subject variability. He cited the variable response of patients to COVID as a case-in-point. There was no evidence of adverse granuloma, necrosis (e.g., no acute toxicity), tumor formation or infection. More details are provided in the complete histopathological report that is included in the appendix (REC-020).

Below is a representative histological image (Trichrome Stained), identifying the fibrous capsule and small vasculature with red blood cells (RBCs). The small blood vessels are indicative of a well received implant with a thin fibrous capsule. The gold wires of the Basmati Injectrode are also pointed out, with an image of higher magnification showing the individual RBCs within the vascular lumen, along with collagen fibers - indicative of stable integration and a normal fibrotic response.

[figure not shown]

Figure 2: Representative histological image of a cross-section of the gold wires of an Basmati style Injectrode indicating key histological features (Fibrous Capsule, Vasculature - Lumen and Red Blood Cells). A higher magnification insert to the right shows a blood vessel lumen and RBS's, indicative of a readily integrated device.

2.0 OBJECTIVES

Success of this study is defined based on primary and secondary outcome measures. These are provided with greater detail below.

2.1 Primary Outcome Measures: Safety

Primary measures focus on device safety and will include the verification of the absence of unexpected inflammation and minimization of excessive encapsulation around the Injectrode as verified by cell staining and pathohistological analysis. Fluoroscopic imaging will be used to document positioning of the Basmati Injectrode lead.

2.2 Secondary Outcome Measures: Interfacing Efficacy

Secondary measures focus on device effectiveness. These will include impedance and stimulation threshold measurements for subcutaneous afferent nervous tissue.

3.0 DEVICE

3.1 Neuronoff Basmati Injectrode insert

This Clinical Non-Significant Risk (NSR) Study will focus on the placement, interfacing with and histopathological assessment of the Basmati Injectrode.

The Basmati Injectrode insert (figure 3) is a mesh formed from gold wire of 99.99% purity, a widely used material in medical devices, offering excellent biocompatibility combined with chemical, mechanical and electrical longevity when implanted into the human body^{8 9 10 11}. The conductive mesh is fabricated from wire with a nominal diameter of 25 microns and at a size of 4 mm width by 10 mm length at about 1.75 mm thickness. This size is similar to a cooked grain of basmati rice.

[figure not shown]

Figure 3: Basmati Injectrode insert is about the size of a grain of rice.

⁸ Geddes, L.A., Roeder, R. Criteria for the Selection of Materials for Implanted Electrodes. *Annals of Biomedical Engineering* **31**, 879–890 (2003). <https://doi.org/10.1114/1.1581292>

⁹ Hielm-Bjorkman A, Raekallio M, Kuusela E, Saarto E, Markkola A, Tulamo RM. Double-blind evaluation of implants of gold wire at acupuncture points in the dog as a treatment for osteoarthritis induced by hip dysplasia. *Vet Rec.* 2001;149(15):452-456.

<https://doi.org/10.1136/vr.149.15.452>

¹⁰ Product: Soft Tissue Marker, Composed of 99.95% Gold
https://www.accessdata.fda.gov/cdrh_docs/pdf3/k031206.pdf
https://www.accessdata.fda.gov/cdrh_docs/pdf9/K091645.pdf

¹¹ Product: Gold Eyelid Weight Implants, Composed of 99.99% Gold
https://www.accessdata.fda.gov/cdrh_docs/pdf/K971242.pdf
https://www.accessdata.fda.gov/cdrh_docs/pdf15/K150986.pdf

The Basmati Injectrode insert will be provided, loaded inside a delivery system to be attached to a standard 3mL luer lock Syringe. The Basmati Injectrode System Assembly (F-0001, see Figure 5A and 5B) is made of materials and components that are FDA listed from qualified suppliers, and will have limited duration of contact with study participant tissue. The materials along with all other device-contacting manufacturing materials are easily cleaned and sterilized following validated processes. The device assembly will be delivered clean, and sealed in a Steam sterilization tyvek pouch placed in a padded box with the appropriate labels. The device will be sterilized using a recommended and validated steam sterilization cycle. The Basmati Injectrode will be placed into the body by a cannula-based delivery device following a stab incision. Removal of the retaining clip (C-0002) readies the device for injection from the cannula (C-0001) into the surgical site.

Figure 4: Basmati Injectrode System Assembly in a sterilization pouch (without label)

During the surgical procedure, the Basmati Injectrode is ejected from the delivery device after introducing the cannula into a subcutaneous tunnel first created by blunt dissection. Creating the skin opening with sharps, a channel via blunt dissection and deploying the Basmati Injectrode is a procedure that can be achieved in under 10 minutes of surgical time.

[figure not shown]

Figure 5: Delivery device attached to a standard 3mL syringe (A) and the Basmati Injectrode ejected from the delivery device (B)

The Basmati InjectrodeTM is indicated for the investigational use for the assessment of chronic biocompatibility, electrical interfacing and neurostimulation data in humans. The investigational devices used for this study will be sourced from Neuronoff, Inc. and a list of all components is provided in the appendix.

3.2 Regulatory Classification

The Neuronoff, Inc Basmati InjectrodeTM is an investigational device and is not yet classified. However, similar devices (i.e. StimRouter) are identified as Class II by the US FDA.

The sponsor has determined that this qualifies as an early feasibility study of non-significant risk.

4.0 STUDY DESIGN

The proposed study is a prospective, single-center, single-arm, non-randomized design. The study will screen up to 20 subjects for study eligibility and potential enrollment. Up to 10 study participants will be provided with the placement of a Basmati Injectrode insert. The maximal placement duration will be 28 days. Subjects selected to participate in the trial will be solely healthy volunteers without any preexisting condition indicated for treatment. Each subject will be followed during the trial period of approximately 45+/-2 days.

The study will end when the last subject has completed the trial period and exited. The expected enrollment period for this study is approximately 2 months. After exit from the clinical study, subjects will continue to be followed by their physician per standard of care. All device and procedure-related AEs and UPs will be collected and reported per the study protocol.

4.1 Schedule of Events (SOE)

Assessments and Data Collection	Screening and Enrollment	Call for patch removal	Injectrode Placement	Follow-up visits	Efficacy and Explant visit	Post study follow-up
Day (relative vs. Placement)	-5 to -4	-2	0	7 ± 2 14 ± 2	28 (-2 to 0)	48 ± 2
• Eligibility confirmation	✓					
• Medical history	✓					
• Physical exam	✓					
• Informed consent	✓					
• Record demographics	✓					
• Verification of absence of allergy to gold & pregnancy test	✓					
• Confirmation of study eligibility	✓					
• Gold skin patch test placement	✓					
• Removal of skin patch		✓				
• Read skin test patch results			✓			
• Basmati placement procedure			✓			
• Ultrasound & Fluoroscopy image capture			✓		✓ (pre & post)	(✓)
• Recording of images of surgical site / placement location	✓		✓ (post)	✓ (✓)	✓	✓ (✓)
• Remove skin suture(s) if placed during surgery						
• Measure impedance needle to needle connection					✓	
• Measure stimulation thresholds					✓	
• Removal procedure					✓	
• Study participant exit						✓

Table 1: Assessments and data collection

5.0 OUTCOMES

The outcomes of the study are focused on collecting data to determine clinical outcomes of placing the Basmati Injectrode for up to 28 days in healthy study participants to 1) assess tissue responses and, on the last day just prior to explant, 2) collect data describing the quality of the electrical interfacing with the Injectrode from outside of the body, as well as with subcutaneous sensory nerves surrounding the Injectrode insert.

Safety data will also be collected at all visits. Data will be collected using:

- True color images of the surgical site and the insert placement location.
- Ultrasound and fluoroscopy (x-ray) images of the insert placement location.
- CRFs to capture any pain or discomfort, AEs and UPs.
- Patho-histological data from tissue samples collected during the explant procedure (Injectrode with approximately 0.5 to 1mm of naïve tissue in Mohs style procedure).

5.1 PRIMARY SAFETY OUTCOME MEASURES

Primary measures of device safety will include verification of the absence of unexpected inflammation and minimization of excessive encapsulation around the Injectrode as verified by cell staining and pathohistological analysis. Fluoroscopic imaging will be used to document positioning of the Basmati Injectrode lead.

5.2 SECONDARY SAFETY OUTCOME MEASURES

Secondary measures of device effectiveness will include impedance and stimulation threshold measurements for subcutaneous nervous tissue.

6.0 MINIMIZATION OF BIAS

Potential sources of bias in this study may result from selection of subjects, and evaluation of study data. The following methods have been incorporated into the study to minimize potential bias: Subjects will be screened to confirm eligibility for enrollment with defined inclusion/exclusion criteria prior to enrollment. Subject demographics will be collected at baseline on possible differences that may affect the primary objective. All study clinicians, participating site personnel, and the Sponsor's personnel will be trained on their respective aspects of the study using standardized training materials. All study clinicians will be trained on and required to follow the Clinical Investigation Plan.

7.0 INVESTIGATORS

7.1 INVESTIGATOR SELECTION AND RESPONSIBILITIES

In order for the Investigators to participate in the study, they must provide a Curriculum Vitae (CV) demonstrating evidence of sufficient training and experience in the management of study participants with chronic pain. The Investigator's participation in other clinical studies must not present a conflict of interest and will not interfere with the clinical study enrollment, study management or study confidentiality. Each participant must be willing to provide any conflicts of interest details, and must be willing to comply with all federal laws and regulations as well as IRB rules regarding clinical studies.

8.0 STUDY POPULATION

The study will recruit healthy volunteers that pass a thorough general medical exam. Subjects may either be male or female and must meet all of the study's eligibility criteria, which are typical eligibility criteria for early feasibility studies. They will be required to sign an informed consent form prior to being asked to participate in the study, undergoing any study-related procedures or having any data collected. It is expected that up to 20 subjects may be screened to be enrolled based on eligibility, and up to 10 subjects will undergo minimally invasive surgery to implant the Basmati Injectrode.

8.1 Inclusion Criteria

To be eligible for this study, study participants **MUST**:

1. Sign a valid, Institutional Review Board (IRB)-approved informed consent form (ICF) and understand the study requirements.
2. Be 18 years of age or older when written informed consent is obtained.
3. Be in good physical and mental health as assessed by a general practitioner.
4. Be able to tolerate electrical stimulation (TENS).
5. Be willing and able to understand and comply with all study-related procedures during the course of the study.

8.2 Exclusion Criteria

To be eligible for this study, study participants **MUST NOT**:

1. Have a cognitive impairment or exhibit any characteristic that would limit the study candidate's ability to completely understand and sign a valid, IRB-approved informed consent form.
2. Have a positive pregnancy test (conducted during enrollment).
3. Have a positive Allergic reactivity to Gold skin test (conducted during enrollment).
4. Show symptoms indicative for Covid19 as assessed during enrollment.
5. Have a skin condition at the planned surgical location.
6. Have a blood coagulation disorder or other indication with the potential to impact the study biocompatibility data in unpredictable ways.
7. Have a medical condition that is a contraindication for minimally invasive surgery.
8. Be implanted with a cardiac defibrillator or pump.
9. Have a history of cardiac arrhythmia with hemodynamic instability
10. Be implanted with a neurostimulator.
11. Have any active electrical implant of any other kind.

12. Have metal implants (particularly in hip).
13. Have active infection.
14. Have allodynia.
15. Take regular use of antiplatelet medications (e.g. aspirin, ticlopidine (Ticlid), clopidogrel (Plavix), tirofiban (Aggrastat) or eptifibatide (Integrilin)).
16. Have untreated drug habituation or dependence.
17. Have uncontrolled seizures (averaging > 2 seizures per month).
18. Currently require, or be likely to require, diathermy and/or MRI during study duration.
19. Have a history of adverse reactions to local anesthetics (e.g. lidocaine).

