9.1.6 INSERT PLACEMENT VISIT (IN-PERSON, day 0)

The Insert Placement Visit begins with an examination of the study participant's arm to capture and interpret the result of the gold allergy skin test by the physician. Once the absence of a gold allergy is verified, the participant advances to the group of up to 10 participants that will receive the Basmati Injectrode insert.

Appropriately trained field staff will assist as necessary with the Basmati Injectrode insert procedure. The recommended placement location for the device on the left or the right hip region (figure 6) will be determined by the physician and documented on the CRF.

[figure not shown]

Figure 6: Depiction of the surgical location (arrows). Placement of the Basmati Injectrode is the hip region of the study participant at approximately the height of the naval.

Prior to the placement of the insert, the surgical location near the hip, approximately at the height of the naval, is cleaned and sterilized following standard OR procedures (betadine, 70% isopropyl alcohol). Following an injection of subcutaneous lidocaine (1%), a small (~5mm) incision is made using a scalpel followed by blunt dissection of the subcutaneous tissue. Blunt dissection technique is used to create a tunnel of about 3-5 mm diameter, at a depth of approximately 2mm measured from the surface of the skin, and up to 2 cm long (figure 7, A).

[figure not shown]

Figure 7: Approximate dimensions of the tunnel placed at the hip region prior to (A) and following (B) the placement of the Basmati Injectrode insert.

Using the deployment device, the Basmati Injectrode is placed into the distal end of the tunnel, leaving a length of approximately 1 cm of empty tunnel between the Basmati and the skin incision (Figure 7, B). At the clinician's discretion, pressure to the wound channel alone or surgical glue may be used to ensure proper adherence of the tunnel walls to close the length of the tunnel. The skin incision may be

closed with steri-strips, surgical glue or one or more small suture loops as per the physician's discretion.

Pain management will be provided post surgery based on physician discretion.

Information regarding the devices used, location and procedure data will be collected on an Insert placement section of the CRF. With the study participant's and the surgeon's consent, Neuronoff's representative may be present during the insert procedure.

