9.1.8 EFFICACY & EXPLANT VISIT (IN-PERSON, day 28)

This visit has two parts. The total duration of this visit is expected to be approximately 1 hour.

The first part of the visit is focused on capturing stimulation thresholds of cutaneous afferent nerves to provide information about the Injectrode's capabilities to conduct current at low electrical impedance values. This first part is anticipated to last for approximately 30 minutes and scheduled to occur just before the explant of the Basmati Injectrode insert.

The second part of the visit is the actual explant of the device that will then be sent to histopathology for further processing. This second part is anticipated to last for approximately 30 minutes and will include image capturing for purposes of documentation.

Part I: Impedance and stimulation threshold data acquisition

Materials:

Stimulation will be provided using a DS7A Constant Current Stimulator unit (Digitimer), a device with CE and FDA clearance. Electrical impedance will be measured with a handheld, battery-powered oscilloscope (Fluke ScopeMeter) that is certified and calibrated. Sterile clinical grade standard needles intended for single patient use (30 gauge) will be used to directly interface percutaneously with the Injectrode. Details for this interfacing approach are provided below. A clinical grade, disposable, surface patch electrode will be used as a distal return, referred to as a TENS electrode/patch in this document. The Stimulator, Oscilloscope, Needles and TENS electrodes will be connected together using standard leads (Pamona, Comed).

Methods:

The setup for these stimulation and impedance tests are done under two types of visualization. First, visualization is done via ultrasound according to a Mohs' surgery plan. Second, the setup is visualized with fluoroscopy to ensure that the needles are placed precisely within the subcutaneously implanted Basmati Injectrode.

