In **measurement 4** (Figure 8d), needles A and B will be connected together to one output/input, while the TENS surface patch electrode (C) will be hooked up to the other output/input of the stimulator and oscilloscope.

[figure not shown]

Figure 8d: Stimulation setup of electrodes for measurement #4.

Measurement 5: Lastly, needles A and B will be hooked up to the stimulator as shown in Figure 8e. Electrical stimulation at the stimulus activation threshold will be applied. The study participant will be asked if they still perceive the stimulation at threshold. If they do not, another stimulus activation threshold test will be performed (e.g. step size amplitude = 100 μ A, pulse width = 200 μ sec) up to 10 mA of current. After each stimulation, the study participant will be asked if they perceived the stimulation, with perception noted as the stimulus activation threshold of current passing through the injectrode. It is expected that the threshold in Measurement 5 will be at least five times higher than that recorded in Measurement 1, as a result of the conductive injectrode shunting (short-circuiting) current between the two needles, thus making it harder to stimulate nerves near the Injectrode. Recorded data from the oscilloscope will be used to calculate the impedance of the Basmati Injectrode.

[figure not shown]

Figure 8e: Stimulation setup of electrodes for measurement #5.

The resulting table of amplitudes and pulse widths resulting from each measurement will be recorded in the CRF.

This closes part 1 of the efficacy and explant visit. The skin at the location of the Injectrode will now be cleaned once more and prepared for surgical removal of the Basmati Injectrode insert.

Part II: Explant (Device Removal)

Methods:

The explant surgical plan will be verified with images from ultrasound and fluoroscopy taken earlier the same day. The explant is a Mohs style surgery. The injection site is anesthetized via lidocaine (solution 1%), and a sharp cut is made above the Basmati Injectrode. Next, tissue forceps are used to hold onto the device while dissection is performed around the Injectrode in naïve tissue at a target distance of about 0.5 to 1 mm.

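### The only scheduled pregnancy test is 30 to 33 days old at the two x-ray fluoroscopy sets of the explant visit, and no retest is planned

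*Protocol*

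**What the plan says.** - **Who may enter.** Sections 8.0 and 8.1 admit men and women from age 18. Neither 8.1 nor 8.2 contains a contraception requirement.
- **Pregnancy test.** Under section 8.2, criterion 2, a participant must not "Have a positive pregnancy test (conducted during enrollment". In section 4.1, Table 1, the row "Verification of absence of allergy to gold & pregnancy test" has one tick, in the screening column (day -5 to -4). Tables 2 to 6 repeat this.
- **X-ray.** Section 5.0 lists "Ultrasound and fluoroscopy (x-ray) images of the insert placement location" among the data collected, so fluoroscopy here is x-ray. The Table 1 row "Ultrasound & Fluoroscopy image capture" is ticked at placement and, as pre and post, at explant. It is bracketed at the final visit.
- **Site imaged.** The Figure 6 caption in section 9.1.6 reads "Placement of the Basmati Injectrode is the hip region of the study participant at approximately the height of the naval".
- **Explant visit, section 9.1.8.** Two kinds of imaging are used before the needle measurements: "First, visualization is done via ultrasound", and then "Second, the setup is visualized with fluoroscopy to ensure that the needles are placed precisely within the subcutaneously implanted Basmati Injectrode". In Part II, "The explant surgical plan will be verified with images from ultrasound and fluoroscopy taken earlier the same day". After removal the site is imaged again by both methods.

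**The concern.** The sponsor chose to keep pregnant women out, and then fixed a schedule in which the check comes about a month before most of the firm x-ray exposure. A negative result on day -5 or -4 says nothing about conception after that day, and it may miss a pregnancy too early to detect.

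The exposure has no clinical purpose for the participant. Section 4.0 describes healthy volunteers with nothing to treat, and the fluoroscopy documents device position and guides study needles. Followed exactly as written, the schedule would x-ray an unrecognised pregnancy without anyone having looked for it. The protocol's own severity scale (section 10.1, Table 7) names harm to a fetus, yet nothing in the visit plan would detect a pregnancy after screening.

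**Working it through.** The protocol states no figure for the age of the test, so there is none to reproduce. The check is date arithmetic.

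**Inputs**
- Test day: -5 or -4 (sections 4.1 and 9.1.3).
- Placement: day 0 (section 9.1.6).
- Explant: day 28 with window -2 to 0, so day 26 to 28 (section 4.1).
- Final visit: day 42 ± 2 (section 9.1.9 and Tables 4 to 6) or day 48 ± 2 (Tables 1 to 3). The protocol gives both, so both are carried.

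**Formula:** age of test = day of fluoroscopy minus day of test.

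| Fluoroscopy | Shortest | Longest | Age of test |
|---|---|---|---|
| Day 0 | 0 - (-4) = 4 | 0 - (-5) = 5 | 4–5 days |
| Explant visit, before and after removal | 26 - (-4) = 30 | 28 - (-5) = 33 | 30–33 days |
| Final visit, day 42 ± 2, if imaged | 40 - (-4) = 44 | 44 - (-5) = 49 | 44–49 days |
| Final visit, day 48 ± 2, if imaged | 46 - (-4) = 50 | 50 - (-5) = 55 | 50–55 days |

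There are three firm image sets: one on day 0 and two at explant. Two of the three follow a test that is 30 to 33 days old.

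**Effect of a retest**
- On day 0 only: still 26 - 0 = 26 to 28 - 0 = 28 days old at explant, so this does not close the gap.
- At the explant visit, before the first fluoroscopy: 0 days old at both sets.

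**Do existing safeguards close the gap?**
- The day 7 and day 14 contacts (section 9.1.7) include no pregnancy check. The second takes place on day 12 to 16, which is 26 - 16 = 10 to 28 - 12 = 16 days before explant.
- Adverse event questioning is general and non-directed (section 10.1).
- Early explant at the investigator's decision (section 1.4) and study exit for meeting an exclusion criterion (section 9.1.9) both help only once a pregnancy is known.

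None of these would detect an unrecognised pregnancy.

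**The case against.** The strongest reply is that criterion 2 is an entry criterion, dated to enrollment, and that the screening test meets it in full. That is correct. A reader might infer that the schedule fails to enforce the protocol's own pregnancy exclusion. The text does not support this, because it states no continuing exclusion at each exposure. What remains is a missing safeguard.

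Other points on that side:

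- **Unseen documents.** The consent form, the case report form, the non-significant-risk document and the risk management procedure are listed in section 18.1 but not shown. They may carry contraception advice, a duty to report pregnancy or a check before imaging. This stands, so the point is limited to the protocol's own schedule and visit descriptions. Advice elsewhere would not put a test into the schedule.
- **No demonstrated harm.** At most 10 people receive the device. Sex mix, contraceptive use, beam field and screening time are not given, so neither the probability of an unrecognised pregnancy nor the fetal dose can be computed. The insert lies just under the skin to one side, and exposure of the uterus is not established. This stands and keeps the point modest.
- **Contact during placement.** A reader might infer that nobody sees the participant in person between placement and explant. The heading of section 9.1.7 allows calls, but the schedule also ticks surgical-site images at follow-up. That suggests attendance, although remote photographs are possible. The point does not depend on this, since neither form of contact includes a pregnancy check.
- **Early explant.** It shortens the interval. The range of 30 to 33 days holds only for explant in the scheduled window.

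**Conclusion.** The point holds as a gap in the fixed schedule. With explant on day 26 to 28, the only pregnancy test is 30 to 33 days old at both explant-visit fluoroscopy sets, and 44 to 55 days old at the bracketed final image if that is taken. The protocol contains no retest and no contraception rule, so a pregnancy that begins or becomes detectable after screening would not be found before the exposure.

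It is neither a contradiction nor evidence of a measurable level of harm, and it does not affect the statistical analysis. The case for change is that the exposure is study-only, the participants are healthy volunteers, and one inexpensive test at a visit already held in person closes the gap. The conclusion assumes that participants of childbearing potential are enrolled, that explant takes place on schedule, and that the bracketed tick means an optional image.

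**What to change.** **Change**
1. For participants of childbearing potential, add one urine pregnancy test at the explant visit, before the first fluoroscopy. Add one before the final-visit image only if that image is taken. Tick both in the schedule of events.
2. If the explant-visit test is positive, omit both fluoroscopy sets and skip the Part I needle and stimulation measurements, recording the reason. Continuing Part I under ultrasound alone is not advisable. It is elective study stimulation of up to 10 mA, and the protocol does not limit its reason for excluding pregnancy to radiation.
3. Leave explant to the investigator's clinical judgement, using the ultrasound already specified for that visit. If the final-visit test is positive, omit fluoroscopy there.
4. State in section 9.1.8 that these omissions are allowed, so that they are not reported as protocol deviations under section 11.1.

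A further test on day 0 is optional, since the screening test is then only 4 to 5 days old.

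**Cost**
- At most 10 × 1 = 10 urine tests, or 10 × 2 = 20 if every participant has the final image, at visits already held in person, plus a schedule row and case report form wording.
- In a rare positive case, that participant's impedance and threshold data (the secondary outcomes, section 5.2) are lost: 1/10 = 10% of the participants with such data if all 10 places are filled. The explant plan would also be verified by ultrasound alone.
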